E2C2 / 18-007779

Enhanced, EHR-facilitated Cancer Symptom Control (E2C2)
Pragmatic Clinical Trial

NCT03892967

Document Date: 03/04/2025

IRB Minimal Risk Protocol Template

General Study Information

Principal Investigator: [name], MSCE

Study Title: Enhanced, EHR-facilitated Cancer Symptom Control (E2C2) trial

Protocol version number: March 4, 2025 Version 24

Research Question and Aims

Hypothesis: Collaborative care management for control of moderate or worse sleep disturbance, pain, physical function impairment, anxiety, depression, fatigue (SPPADE symptoms), and physical dysfunction among cancer survivors and patients with cancer will improve quality of life, symptom severity, and adherence to cancer treatment, and will also reduce need for acute care.

Aims:

Specific Aim 1. Conduct a cluster randomized pragmatic trial with a stepped wedge design to test the hypothesis that a symptom control-focused E2C2 intervention will significantly reduce SPPADE symptom and physical dysfunction scores; reduce unplanned hospitalizations, emergency department (ED) visits, and intensive care unit (ICU) admissions; improve adherence to cancer therapies; and improve self-reported quality of life.

H1a. SPPADE symptom scores will improve more, relative to prior scores, for patients who have been exposed to the intervention when compared with the improvement of patients that are not exposed.

H1b. Among patients who report moderate or worse symptoms, SPPADE symptom scores will improve more for patients who have been exposed to the intervention when compared with the improvement of patients that are not exposed.

Specific Aim 2. Evaluate the hypothesis that use of a multifaceted, evidence-based implementation strategy to support adoption and use of the E2C2 system will result in improvements in implementation and clinical outcomes.

Specific Aim 3. Conduct a mixed methods evaluation to detect, understand and reduce disparities in the adoption and implementation of the E2C2 intervention among elderly and rural-dwelling patients with cancer.

Background:

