The SCM will contact patients in response to ePRO *symptom-triggered* alerts and trend reports. Patients will be able to view a short video (SCM Intro Video) explaining the role of the SCM when they are completing their BSFS questionnaire and indicating whether they'd like the assistance of a nurse Symptom Care Manager. In efforts to create awareness of the SCM role, patients will have the opportunity to receive a printed "face sheet" with photos of the SCMs and details on their role and how to request intervention materials. The E2C2 Face Sheet will be handed out by clinical Oncology staff. The SCM will monitor trend reports weekly, respond to automated monitoring clinical alerts and patient calls daily, configure orders for the oncology care team via the Epic EHR, and serve as the "triangulating" lynchpin between patient and the oncology care team (including the supervising oncologist). The Symptom Care Managers will assess patients' needs for resistance band and pedometer (up to 2 pedometers per patient) interventions/therapies and will request these for the patient via Clinical Research Coordinator who will mail the items with the IRB approved cover letter and patient education materials. For patients who have a local Oncologist in addition to being seen by Mayo Oncology, the Symptom Care Manager will send a letter to the local Oncologist (if there is a current authorization to do so). This letter will contain information outlining the SCM's involvement with the patient and the discussed action plan for the identified symptom(s). For E2C2, the SCM, Social Worker and Physical Therapist will have weekly case management sessions with the Palliative Care Service physician to review new Level 2 patients and patients not responding to therapy. In addition, the Clinical Research Coordinator will send a portal message to 2 groups of patients: a group who requested contacted from a Symptom Care Manager (SCM) and a group without SCM contact. This message will include a link to patient education material and to Mayo Clinic Connect.

Implementation Bundle

Implementation Strategies. The Implementation Bundle will be initiated at the same time as the Symptom Control Bundle as part of the stepped-wedge design.

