for medications, or clarify which of the many candidate measures should be considered.¹²¹ We will therefore assess adherence broadly and examine the frequency of missed imaging, medical oncology clinic visits, and chemotherapy appointments. Additionally, we will capture any unplanned hiatuses in cancer treatment or dose reductions. This information is routinely recorded on electronic chemotherapy administration forms from which discrete structured data elements can be abstracted. For oral hormonal regimens we will use the accepted definition of at least 80% of recommended doses to create a binary variable.¹²² [name] (E2C2 Co-I) has contributed seminally to the literature on adherence to breast cancer adjuvant therapies.^{123,124} We will apply this criterion to oral chemotherapy and immunotherapy as well.

Vital status. Vital status will be verified through death certificates, the Mayo Clinic EMR, next-of-kin reports, the Mayo Clinic Tumor Registry and the Social Security Death Index website.

Reporting mode and rates. Patient reported outcomes will be collected via several modes for the E2C2 trial. These include remote modes; the patient portal and interactive voice response, and point of care modes; tablets and provider entry via Epic Care. Data regarding patients' mode of PRO reporting are automatically stored by the Epic EHR. We will perform descriptive statistics to characterize how reporting modes differ across subgroups defined by demographic, clinical, cancer-related, and symptom characteristics. Additionally, we will create uni- and multi-variate mixed models to estimate associations of reporting frequency and mode with patient characteristics.

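### The secondary adherence outcome takes in treatment hiatuses and dose reductions without separating prescriber-ordered changes from patient non-adherence, so a difference in those items cannot be read as a change in adherence

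*Combined protocol and SAP*

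**What the plan says.** Specific Aim 1 lists, among the effects expected of the intervention, that it will "improve adherence to cancer therapies". The measures are set out under Endpoints, Secondary, Cancer treatment adherence, where the plan notes that the literature offers no settled definition and chooses a wide one. There are three groups of items:

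- Missed appointments: "We will therefore assess adherence broadly and examine the frequency of missed imaging, medical oncology clinic visits, and chemotherapy appointments".
- Interruptions and reductions: "we will capture any unplanned hiatuses in cancer treatment or dose reductions". On the source it adds: "This information is routinely recorded on electronic chemotherapy administration forms from which discrete structured data elements can be abstracted".
- For oral hormonal regimens, the threshold is "at least 80% of recommended doses to create a binary variable". It then says: "We will apply this criterion to oral chemotherapy and immunotherapy as well".

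The plan does not record the initiator of, or the reason for, a hiatus or reduction, and plans no sensitivity analysis on the matter. It does not say whether the items are combined, and it names no model for adherence.

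**The concern.** Adherence ordinarily means that the patient follows the treatment as prescribed. A dose reduction is normally the prescriber's decision, and so are many unplanned holds. A patient who follows a reduced prescription is adherent, yet would register an event under the second group of items.

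If this misclassification were equal in both conditions it would mainly add noise. Here it may not be equal. What clinicians know about symptoms, and how often they learn it, changes when a cluster crosses over. Ordered changes could therefore move with intervention status even if patients behave exactly as before. At stake is the reading of one hypothesised secondary benefit: a shift in prescribing could be reported as a gain or a loss in adherence.

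**Working it through.** The documents state no event rate, effect size or power for adherence, so there is no figure to reproduce. The check is first textual and then illustrative.

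**1. Do the qualifiers isolate patient behaviour?** The word *unplanned* removes scheduled treatment breaks. It does not remove a hold that the prescriber orders because of toxicity, since that was not planned either. Dose reductions have no qualifier. By contrast, the Health care utilization section collects whether a hospital admission was planned or unplanned and where an unplanned one started. Reductions and hiatuses have no matching split by initiator.

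**2. Can ordered changes differ by condition?** Three features begin at go-live:
- Symptoms are assessed more often, most of all in symptomatic patients (Automated Symptom Monitoring).
- Symptom intensity is placed in clinicians' notes and a graphic view (Presentation of symptom data to patients and clinicians), and point-of-care advisories start (Point-of-Care Computer Reminders).
- Care managers contact patients after symptom alerts and liaise with the oncology team (Nurse Symptom Care Manager section).

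Greater visibility could raise ordered changes by revealing toxicity. Better symptom control could lower them; the Background itself ties poor symptoms to non-adherence with treatment. The direction is open.

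**3. How much could this matter?** This uses a hypothetical measure, any event of either kind. It is not an endpoint that the plan defines. Every rate is assumed, and the two sources are taken as independent. With p the patient-driven proportion and c the prescriber-ordered proportion, any-event = 1 − (1 − p)(1 − c).

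Control, p = 20%, c = 20%: 1 − 0.80 × 0.80 = 36.0%.

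| E2C2 condition | Calculation | Any-event | Change (points) |
|---|---|---|---|
| p 20%, c 24% (+20% relative) | 1 − 0.80 × 0.76 | 39.2% | +3.2 |
| p 20%, c 18% (−10% relative) | 1 − 0.80 × 0.82 | 34.4% | −1.6 |
| p 16% (−20% relative), c 20% | 1 − 0.84 × 0.80 | 32.8% | −3.2 |
| p 16%, c 24% | 1 − 0.84 × 0.76 | 36.2% | +0.2 |
| p 16%, c 18% | 1 − 0.84 × 0.82 | 31.1% | −4.9 |

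Rows 1 and 2 show an apparent loss and an apparent gain with no change in patients. Row 4 shows a true gain hidden, and row 5 a true gain inflated.

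Over p of 10% to 20% and control c of 10% to 30%:
- With p unchanged, a 10% to 30% relative rise in c adds 0.8 to 8.1 points.
- With p unchanged, a 10% relative fall in c removes 0.8 to 2.7 points.
- With p cut by 20% relative, the benefit disappears once c rises by about 5% (p 10%, c 30%) to 43% (p 20%, c 10%) relative.

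**4. The 80% rule.** The plan does not say whether recommended doses means the starting regimen or the regimen in force. Suppose an ordered hold removes a fraction h of the starting doses and the patient takes all the rest. Against the starting regimen the ratio is 1 − h, which fails the rule once h exceeds 1 − 0.80 = 0.20. Against doses prescribed at the time the ratio is 1, and the patient passes. The same patient can be classed either way.

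**The case against.** The plan acknowledges that there is no agreed definition and sets out to measure adherence broadly. Aim 1 speaks of adherence to therapies and does not expressly limit this to patient behaviour, so delivery of the intended regimen is a coherent reading. The items are listed rather than pooled. If they are reported one by one, a rise in dose reductions cannot offset a fall in missed appointments. The structured forms may already hold a reason for each change. The instruments are the same before and after go-live, and the symptom screen is standard of care in both conditions, so the effect on prescribing is conjecture.

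Much of this stands. The missed-appointment items are untouched, and the percentages above illustrate a mechanism only. Two stronger inferences fall with it:

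- A reader might infer that E2C2 will make adherence look worse. The documents support no direction.
- A reader might infer that care managers' queued orders, described as "configure orders for the oncology care team via the Epic EHR", themselves change cancer treatment. The sections on order pre-configuration and on Level 2 care describe symptom-directed orders, so the argument rests on symptom visibility and contact with the team.

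What remains is that reductions and hiatuses, even reported alone, sit under the adherence heading with both sources mixed, and the plan does not commit to using a reason field if one exists. If delivery of the intended regimen is meant, it is a different outcome and should be named as such.

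**Conclusion.** The point holds, and it is minor. A between-condition difference in unplanned hiatuses or dose reductions cannot be read as a change in adherence, because prescriber-ordered changes are included and may vary with intervention status. The size and direction cannot be fixed from the documents. The conclusion assumes only that some of the recorded changes are ordered by prescribers and that greater symptom visibility or better symptom control could alter how often.

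A reader might go further and say that the trial cannot answer its adherence hypothesis. That is not supported: the missed imaging, visit and chemotherapy-appointment items remain usable, and the primary SPPADE analysis is unaffected. A reader might also infer that the 80% cut-off changes meaning for infrequent infusions. That requires taking immunotherapy to include infused agents, whereas the sentence can equally mean oral agents only, and the documents give no dosing schedule or observation window for the rule. This is an ambiguity to resolve, not a demonstrated fault.

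**What to change.** Amend the adherence section of the plan as follows:

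1. Keep missed appointments and patient-driven interruptions as the adherence measures.
2. Report prescriber-ordered dose reductions and holds as a separate treatment-modification outcome with no hypothesised direction, using the initiator or reason where the administration forms or orders record it.
3. Compute the 80% rule against doses prescribed at the time, so that an ordered hold or reduction is not counted as doses not taken.
4. State whether immunotherapy in that rule means oral agents only.
5. State whether the items are analysed separately or combined.

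The cost is some wording and one more abstracted field. No data are discarded and no patient's treatment changes. The downside is that events with no recorded initiator must be shown as unclassified, by condition, and if they are numerous the split will be less informative.
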